A key issue in many settings, including ours, is that testing falls into a separate budget from the treatment of patients with CDI infections. This has the potential to distort the decision of whether to run a test and, if so, what sort of test. The distortions are of two types. First, the hospital may decide to order more tests than is optimal, since the tests are perceived as "free" from the perspective of decision-makers. At the same time, the diagnostic facility may choose low-cost, slow diagnostics, because the costs associated with delays in test results are borne by the hospital. This is a classic case of silos in health care costs inefficiently distorting policy decisions, with potentially negative results for both patient health and costs.

Many institutions follow the clinical practice guidelines provided by the Infectious Diseases Society of America for the management of *C. difficile* (Cohen et al., 2010). As part of routine Infection Prevention and Control (IPC) management, patients with acute diarrhea of unknown cause are pre-emptively placed in private rooms with additional contact precautions, which mandate the use of gowns and gloves for healthcare workers. This is also known as patient isolation. Investigation for gastrointestinal pathogens is typically initiated and the duration of patient isolation depends largely on the result of microbiological testing. When severe or complicated CDI is suspected, patients are initiated on empiric treatment as soon as the diagnosis is suspected. Generally, oral metronidazole is used for mild-to-moderate CDI and oral vancomycin for severe CDI. Among hospitalized patients with acute diarrhea, initiation of pre-emptive management for CDI is common. With requested CDI screening, 85% are negative on GDG screen and 89% are negative post PCR confirmation.

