This study is a cross-sectional CRXO in that, each cluster-period consists of different individuals (patients). The order in which the interventions are delivered to each cluster (ward) is randomized to control for potential period effects. Within Foothills Hospital there are 40 wards which will be observed over a 12-month period. Each ward is randomly assigned to administer one of the two interventions for the first 6-month period (Period 1). In the second 6-month period (Period 2), the ward will administer the other intervention. Within each ward (cluster) there are two cluster-periods. Study outcomes during Period 1 and Period 2 intervention will be compared in both arms (NPT and centralized laboratory testing).

NPT testing can deliver results within several hours, while typically off-site testing takes one to two days. If NPT and the off-site testing deliver identical test results as our pilot data suggest, we can follow the clinical outcomes for each arm without the confounder of differences in test performance. As a contingency, if variation in test performance characteristics is found, analysis of patient outcomes will take this into consideration.

For patients without CDI, the antibiotics, and in many cases, the isolation, are unnecessary. NPT testing has the potential to avoid this unnecessary use of antibiotics and to avoid costly isolation procedures for the day+ that standard testing requires. It also enables a better-directed diagnostic process for the cause of diarrhea. For patients who are positive for CDI, the earlier test result will influence downstream events such as initiation of antibiotic therapy, resolution of disease, hospitalization days, and other clinical outcomes.

We hypothesize that NPT for CDI will result in reduced patient isolation days in the hospital, decreased morbidity and mortality, reduced unnecessary antibiotic use and overall reduced costs to the health care system, including both hospital and laboratory.

Previous data has indicated that the mean number of patients a ward is 39/month ($SD=43$) for a total of 1578 patients in a 6-month period and the mean number of negative patients is 33/month ($SD=34$) for a total of 1300 negative pts in a 6-month period. The inclusion criteria will be diarrhea in adult patients admitted to four acute care hospitals in the Calgary region being tested for CDI. Outpatients and patients in the emergency room will be excluded.

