Our primary endpoint is to examine the differential effect of NPT on the duration of contact precautions (i.e. patient isolation days). Secondary outcomes will compare turn-around times from specimen submission to result, days of hospitalization, the number of days of antibiotic therapy, the incidence of CDI, severe CDI, and in-hospital mortality. A comprehensive economic evaluation will be performed to determine the cost of testing, patient isolation, and hospitalization for all patients in the control and treatment arms.

Methods:

Contact precautions (i.e. patient isolation) due to CDI will be defined as an order by healthcare workers for contact precautions within the 7-day infection window of a CDI diagnosis. The length of time on contact precautions will be defined as the calendar date contact precautions are completed or patient discharge date minus the calendar date contact precautions are ordered. Data on contact precautions will be extracted from the clinical patient management system in Calgary, known as Sunrise Clinical Manager (SCM). It is used extensively in all Calgary acute care facilities and emergency departments. These data include patient identifiers (e.g. patient health number, names, date of birth), start and stop dates of isolation, facility, and patient care unit where isolation order was placed, and reason for isolation (e.g. CDI, diarrhea). These data will be linked to the specimen results tested for CDI by the patient's Personal Health Number (PHN). Turn-around times from specimen submission to result will be provided by Calgary Laboratory Services. Days of hospitalization will be defined as the difference between the admission and discharge date. The specimen results will be linked to the Discharge Abstract Database using the patient's PHN to determine during which acute care encounter the specimen was collected and the admission/discharge dates of that encounter. Antibiotic therapy will be defined as the administration of antibiotics initiated on the day of and up to 48 hours after specimen collection for CDI testing. Total days of antibiotic therapy during the acute care encounter will be defined as the calendar date antibiotic therapy is completed minus the calendar date antibiotic therapy is ordered. The data will be extracted from SCM.

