We will also account for the severity of CDI. The epidemiological definition for severe CDI is that primarily proposed by Cohen *et al*. This definition has been used by infectious disease specialists in Alberta to guide the management and treatment of patients with CDI. Patients with severe CDI will have leukocytosis with a white blood cell (WBC) count $>15,000$ cells/ μ L OR an elevated serum creatinine (i.e. 200 μ mol/L or greater). The inpatient laboratory results that will be considered to meet the definition for severe CDI will be those collected within a 7-day infection window around the date the laboratory tested positive for *C. difficile*. The presence of either measure meeting the criteria within the defined infection window will qualify as meeting the definition of severe CDI. If either criterion is measured more than once during the infection window, the highest value will be used to represent the severity of CDI. The laboratory values will be provided by Calgary Laboratory Services and linked to the positive *C. difficile* test results. In-hospital, all-cause mortality will be defined as death occurring during the acute care encounter where specimens were collected for *C. difficile* testing.

We predict that, given the large number of patients and randomized study design, matching of patients by age, gender, and co-morbidities is not required. Potential hurdles in the study model are logistical challenges associated with building a testing and reporting system for a hospital on a 24hrs/7 days per week basis. The strength of the proposal lies in the scale and nature of the study which seeks to establish the medical and economic benefit of NPT versus centralized testing. The results could dramatically influence public health policy in this country and seek to bridge traditional silos, namely the laboratory and hospital budgets. Data on costs will be furnished by our partners at Calgary Laboratory Services and Alberta Health Services (Infection Prevention and Control).

Data Analysis:

In order to make the data generalizable to other settings, an appropriate econometric methodology to assess the impact of the impact of the NPT testing through multivariate regression is required. For example, consider the following potential model:

$$y_i = \beta_0 + \beta_1 POCT_i + \beta_2 Z_i + \beta_3 H_i + \beta_4 T_i + u_i$$

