where y_i is the outcome variable of interest (such as the hours that a patient spends in isolation or the days of hospitalization); $POCT_i$ is a dummy variable indicating whether the patient had a NPT test; Z_i is a vector of individual-specific variables, including age, gender, CDI status and severity, and the like; H_i is a set of dummies indicating ward; T_i is a set of dummies indicating season or month; and u_i is an individual-specific error term. This approach allows us to identify the effect of NPT testing independent of patient, ward and season. In addition, the NPTT dummy can be interacted with other variables to see whether the impact of NPT testing is higher for certain types of patients

Beyond evaluating the relative merits of NPT versus centralized testing, studies will also look at the microbiology of CDI in this study. Specifically, we will conduct several laboratory methods to examine antibiotic resistance and genetic variation in CDI. For example, whole genome sequencing of cultured CDI isolates may inform us about the transmission of specific strains in our setting. Indeed, certain strains and states of gut dysbiosis may result in increased morbidity and mortality (Shahinas et al., 2012). We will look at the microbiome of patients in this study to determine if dysbiosis contributes to adverse clinical outcomes. We will also correlate the strain types with the results of testing to determine if genetic variation affects test performance. Cultured toxin-producing CDI isolates will serve as a gold standard to evaluate test performance.

Originality of the proposal:

It is our view that in the clinical laboratory arena NPT for CDI (described earlier) as a technology has already matured to a stage that translation of this technology into the clinical domain is now needed. As described previously, several formats including lateral flow are currently available through major diagnostic companies. The Infectious Diseases Society of America (IDSA) has recently recommended that rapid diagnostic testing can enhance antimicrobial stewardship by promoting appropriate antibiotic use for respiratory infections (Barlam et al., 2016). However, the recommendation is listed as “weak” with “low-quality evidence”.

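### Residual ward-by-period correlation is not handled anywhere in the plan; if the example model is fitted as printed with ordinary standard errors, they are too small whenever such variance remains

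*Combined protocol and SAP*

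**What the plan says.** The Study Objectives section describes a two-period cluster randomised crossover with 40 wards at one hospital: "Each ward is randomly assigned to administer one of the two interventions for the first 6-month period (Period 1"), and the other intervention in the second six months. Different patients contribute to each ward-period. That gives 40 × 2 = 80 ward-periods, each wholly on one form of testing.

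The Data Analysis section offers one regression, introduced by "For example, consider the following potential model". Its terms are an indicator for near-patient testing (NPT), individual covariates (age, gender, CDI status and severity, and the like), ward dummies, and season or month dummies. It adds that "u_i is an individual-specific error term". How standard errors are to be computed is not stated. No section mentions a ward-by-period effect, a clustered variance, a cluster-level summary, an intracluster correlation or a significance level.

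The documents leave open which patients enter the primary analysis. Methods defines contact precautions due to CDI as "an order by healthcare workers for contact precautions within the 7-day infection window of a CDI diagnosis", which points to CDI-positive patients. Study Objectives expects a saving elsewhere: "For patients without CDI, the antibiotics, and in many cases, the isolation, are unnecessary". That points to all tested patients, as does the use of CDI status as a covariate.

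**The concern.** In a crossover of wards, the treatment contrast is made between the two periods of the same ward. Ward dummies remove whatever is constant in a ward over the year. Month dummies remove whatever changes in all wards together. Neither removes a change that affects one ward in one period, such as a staffing change. CDI status and severity would absorb part of the effect of a local outbreak on case mix, but not that kind of change.

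Such a change is shared by all patients of that ward-period, and all of them have the same treatment. A model with independent patient errors counts them as separate evidence. A chance difference between ward-periods could then be read as an effect of NPT. With substantial ward-by-period variance, precision is limited by the 40 wards more than by the roughly 3,000 patients on whom the plan relies.

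**Working it through.** There is no stated power, intracluster correlation or standard error to reproduce, so the check starts from the stated counts.

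**Cluster-period size**
- All tested patients: 1578 / 40 = 39.45 per ward per six months. Study Objectives labels the mean of 39 as monthly, but 40 × 39 = 1560 fits the six-month total of 1578, whereas 40 × 39 × 6 = 9360 does not. The six-month reading is used here.
- CDI-positive patients, from the counts ("for a total of 1300 negative pts in a 6-month period"): (1578 − 1300) / 40 = 6.95.
- CDI-positive patients, from the background share ("89% are negative post PCR confirmation"): 0.11 × 1578 / 40 = 4.34.
- Uneven wards: SD 43 is read as a between-ward SD over six months, which is an inference. The size that matters is then m_eff = m(1 + CV²) = 39.45 × (1 + (43/39.45)²) = 86.3.

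**Assumptions not in the documents:** two-sided 5% test; ρ, the ward-by-period share of the residual variance left after the model's covariates, of 0 to 0.025.

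**Formula.** With ward and time dummies fitted, the true variance of the treatment coefficient is approximately the ordinary variance times

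V = 1 + m_eff · ρ / (1 − ρ),

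and the actual type I error is 2{1 − Φ(1.96 / √V)}. At ρ = 0, V = 1 and the ordinary standard error is correct.

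| Patients analysed | m_eff | ρ | V | √V | Type I error (formula) |
|---|---|---|---|---|---|
| All tested, equal wards | 39.45 | 0.01 | 1.40 | 1.18 | 9.7% |
| All tested, equal wards | 39.45 | 0.025 | 2.01 | 1.42 | 16.7% |
| All tested, uneven wards | 86.3 | 0.01 | 1.87 | 1.37 | 15.2% |
| All tested, uneven wards | 86.3 | 0.025 | 3.21 | 1.79 | 27.4% |
| CDI-positive, equal wards | 6.95 | 0.01 | 1.07 | 1.03 | 5.8% |
| CDI-positive, equal wards | 6.95 | 0.025 | 1.18 | 1.09 | 7.1% |
| CDI-positive, equal wards | 4.34 | 0.01 | 1.04 | 1.02 | 5.5% |
| CDI-positive, equal wards | 4.34 | 0.025 | 1.11 | 1.05 | 6.3% |

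**Simulation.** 10,000 null trials per scenario: 40 wards, 20 per sequence, ward dummies and a period term, ordinary standard errors. Type I error at ρ = 0 / 0.0025 / 0.005 / 0.01 / 0.025:
- All tested: equal wards 5.3 / 6.4 / 7.4 / 9.7 / 16.2%; uneven wards 5.1 / 7.4 / 9.2 / 13.6 / 24.7%.
- CDI-positive, 6.95: equal 5.2 / 4.9 / 5.5 / 5.8 / 6.7%; uneven 5.1 / 5.7 / 6.2 / 6.3 / 9.3%.
- CDI-positive, 4.34: equal 5.0 / 4.6 / 5.2 / 5.2 / 6.2%; uneven 5.2 / 5.3 / 5.5 / 5.7 / 7.5%.

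Monte Carlo error is about 0.2–0.4 points. For uneven wards the formula runs a little above the simulation; the simulated figures are the ones used in the conclusion. With 12 month dummies, as the printed model allows (8,000 trials), the results at ρ = 0.01 and 0.025 were 9.4 and 16.5% (equal) and 14.0 and 25.2% (uneven) for all tested patients. For CDI-positive patients they were 5.2–7.2% and 5.8–9.0%. Skewed errors gave similar values.

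**If the monthly label is taken literally,** m = 39 × 6 = 234. With equal wards and ρ = 0.01, V = 1 + 234 × 0.0101 = 3.36, √V = 1.83, and type I error by the formula is about 29%. The literal label makes the problem larger.

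**The case against.** The printed model is only a possible one, and an individual-level error term in an equation is not a choice of variance estimator: ward-clustered standard errors can be used with exactly this equation. The harm needs two conditions that the documents do not establish, namely that ordinary standard errors are used and that ward-by-period variance remains. All of that stands, and it makes the point conditional. It does not remove it, because no other text supplies a method that respects the level at which treatment is assigned.

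Four stronger readings are tempting and not supported:
- *The plan ignores clustering.* It does not. The ward dummies remove the stable part of the within-ward correlation; only the ward-by-period part is left.
- *The plan prescribes ordinary standard errors.* It is silent on this.
- *The trial's false-positive rate will be about 25%.* That figure needs the highest share assumed here, all tested patients, and SD 43 read as a between-ward six-month SD. If only CDI-positive patients are analysed, the inflation at shares up to 0.01 is hard to tell from none.
- *Secondary outcomes such as turn-around time and length of stay must show the larger inflation.* They are recorded for all tested patients, so their cluster-periods are larger, but nothing says their variance share equals that of isolation days. For turn-around time, where the plan expects hours against one to two days, a null false-positive rate matters little.

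The counts also have loose ends. The 80 ward-periods assume one hospital, while the inclusion criteria name four, and wash-in and wash-out could change the number of patients analysed per ward-period.

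**Conclusion.** The concern holds in conditional form. The plan has no provision for residual ward-by-period correlation, and its one example model, fitted as printed with ordinary standard errors, understates uncertainty whenever such variance remains. If none remains, those standard errors are correct.

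At an assumed share of 0.01, type I error is about 10% (equal wards) to 14% (uneven) for all tested patients and about 5–6% for CDI-positive patients only. At 0.025 it is about 16–25% and 6–9%. These figures illustrate the possible size; they do not estimate it. They rest on an assumed alpha, assumed shares, about 39 patients per ward per six months and, for the uneven case, the reading of SD 43. The point deserves correction before analysis because it bears on the validity of the main comparison and the correction is cheap.

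**What to change.** In the Data Analysis section, keep the ward dummies, add a period term (dummies for the 12 study months contain it; season dummies need not), and base inference for the primary and secondary outcomes on the ward-period level. Either of these would serve:
- a random ward-by-period effect with small-sample degrees of freedom; simulated type I error was 3.2–5.8% over all sizes, shares and error shapes examined;
- ward-clustered standard errors with a jackknife-type correction and a t reference; 4.4–5.7%.

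The small-sample correction matters. Uncorrected cluster-robust standard errors with a t reference gave 4.9–5.9% with equal wards but 6.3–8.1% with uneven ones. Degrees of freedom should reflect the wards with patients in both periods: in the uneven simulation about 38 of 40 for all tested patients, and 28–31 for CDI-positive patients.

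The cost is a paragraph of text and a few lines of code, with no new data. Intervals will be wider if ward-by-period variance exists. If it is zero, the mixed-model test is slightly conservative (3.2–4.1% against a nominal 5%).
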